positive effects in women but not in men (Fox et al., 2012; [name] et al., 2011). Preliminary data also showed that GUA 3 mg/day (bid dosing) vs. placebo led to higher cocaine-negative urines in an 8-week outpatient setting only in women and not men.

4. **Research Plan:** Summarize the study design and research procedures using non-technical language that can be readily understood by someone outside the discipline. **Be sure to distinguish between standard of care vs. research procedures when applicable, and include any flowcharts of visits specifying their individual times and lengths.** Describe the setting in which the research will take place.

The current study will test **GUA (3 mg/day) vs Placebo (PBO)** in a 10-week clinical trial across 2 sites in a total of 100 SUD women.

All participants will be titrated to steady-state medication levels over 2 weeks followed by a **7-week treatment period using a standard cognitive behavioral relapse prevention** with medication management and contingency management (CM) for treatment attendance. A 5-day taper will be implemented in week 10. All participants will also take part in **two laboratory challenge test sessions**: one at pre-treatment (pre-tx) and one during week 9 of treatment, to assess provoked drug craving and cognitive flexibility under stress, drug cue and neutral cue conditions in a randomized and counterbalanced order.

Pre-treatment Intake Procedures: Following the initial telephone screening, eligible participants will meet with the research staff to obtain written informed consent. Subjects will complete 2-3 intake appointments, and during these appointments they will be consented, screened of substance use, and provide demographic and psychiatric data. Physical examinations, blood work, a urine test, and a breathalyzer test will also be completed. All subjects will meet with the study physician, and if deemed eligible, after discussion of risk and benefits, subjects will be randomized into the study.

Randomization: Eligible subjects will then be randomized in a double blind manner to either placebo or 3 mg/day (bid dosing) of GUA balancing the patients on age, education, race, ADHD and severity of drug use.

Medication Titration Period (wk 1-3): Following a 3-day abstinence period, a 2-week titration period, previously found to be safe and with only mild adverse effects (Fox et al., 2014; Fox et al., 2012; Milivojevic et al., 2017) will be initiated (see Table 1).

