Data Management: Data entry will be conducted using the Web-based REDCAP direct data entry system. Both sites are fully trained and running with REDCAP and have implemented this platform in clinical outcome studies with SUD samples. Utilizing the REDCAP system will allow data to be directly collected into the Yale managed web-based system across sites with no identifying information transmitted over the internet. Field validation (e.g. no out of range/invalid responses accepted) and form validation (e.g. logically impossible responses to different questions) are built into the REDCAP system and the study data manager will conduct weekly quality control and data management. After online reviews, the data are archived onto servers and password protected with only certain members of the team having appropriate level of data access. All quality control and management issues will be addressed immediately and also discussed in the across site weekly study meetings.

Data Analysis: Data analysis will be performed under the direction of Project PIs in consultation with [name], the Yale biostatistician. Screening for data entry errors, outlier checks and assessment of missing data and testing of normality assumptions will be conducted. Transformations will be applied as necessary. We will compare the treatment groups on demographic and clinical variables using t-tests/chi-square analyses as appropriate. If any group differences are found, the specific variable will be entered as a covariate in all specific analyses. For the primary outcome, we will use significance level of 0.05. Significance levels for secondary outcomes will be adjusted using Bonferroni correction for number of analyses performed.

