Adequacy of Sample Size: Sample size estimates are limited by the fact that there are no previous clinical outcome studies of GUA/PBO in SUD women. As shown in above, data from our previous work with GUA yielded highly significant sex X med group effects for target engagement measures of drug craving and Stroop improvements with moderate to high effect sizes (f^2 's ranging from 0.39-1.22). Using the GUA/PBO preliminary data from the 8-week pilot trial, percent of negative cocaine urines were 40.18% versus 67.86% in PBO vs GUA for the whole group (large effect size $d=0.76$), with 53.12% versus 100% for PBO vs. GUA in women ($d=1.0$) and 35% vs 55% negative urines in placebo vs guanfacine in men ($d=0.628$). Thus, assuming power=0.80, and at $p<0.05$, α level of 0.05, sample size estimates indicate that we will need 40 subjects per cell (Medgroup) to assess GUA/PBO in clinical outcome hypotheses in Aim 2 and Aim 3. This sample size allows for detection of medium effect sizes ($f=0.25$, Cohen) with more than 80% power assuming α level of 0.05 for the main effect of medication group on the primary outcome variable. Assuming an α level of 0.01 to correct for multiple tests for the secondary outcome measures we can detect effects in the medium range ($f=0.28$) with 80% power for all the main effects for secondary outcome variables. Including a 20% attrition rate, we propose an N=50 per group for a total N of 100 (50 per site).

SECTION II: RESEARCH INVOLVING DRUGS, BIOLOGICS, RADIOTRACERS, PLACEBOS AND DEVICES

If this section (or one of its parts, A or B) is not applicable, check off N/A and delete the rest of the section.

A. RADIOTRACERS

N/A

B. DRUGS/BIOLOGICS **N/A**

1. If an **exemption from IND filing requirements** is sought for a clinical investigation of a drug product that is lawfully marketed in the United States, review the following categories and complete the category that applies (*and delete the inapplicable categories*):

Exempt Category 1: The clinical investigation of a drug product that is lawfully marketed in the United States can be exempt from IND regulations if all of the following are yes:	
1. The intention of the investigation is NOT to report to the FDA as a well-controlled study in support of a new indication for use or to be used to support any other significant change in the labeling for the drug.	

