In the previous work with 3-week treatment of GUA (3mgs/day) versus placebo discussed above, [name] found it to be safe and well tolerated. In the initial study (25), the most common side effects were mild tiredness and fatigue (guanfacine 24%; placebo: 8%) and headaches (guanfacine 18%; placebo 8%). All symptoms dissipated over time without further intervention. Side effects from a dose-ranging study comparing placebo, 2 and 3 mg/day of guanfacine (26) (106) indicated mild symptoms which dissipated rapidly without intervention in 7/21 individuals in the placebo group (33.33%), 5/12 individuals in the guanfacine (2mg) group (41.7%) and 4/11 individuals in the guanfacine (3mg) group (36.4%). Furthermore, there were no significant blood pressure differences across medication and placebo groups. Also, there were no significant sex differences in reported side effects.

In preparation for this proposal, [name] conducted a randomized, double-blind, 8-week pilot study of GUA (3mgs/day) with treatment seeking CUD men and women (n=7: 5M/2F) vs placebo (n=7: 4M/3F). Using the same 16-day titration schedule used previously and proposed in the current project, GUA plasma levels were assessed as at weeks 4 and 8 in the outpatient study as well as in the inpatient study described above. GUA levels obtained in the outpatient pilot were comparable to levels to those from the inpatient study described above. These data suggest that generic GUA with bid dosing was acceptable, and patients showed high medication compliance in the outpatient setting.

Together, data indicates guanfacine 3 mg/day to be safe and tolerable with regard to assessing target engagement and validation across multiple sites in SUD women.

3. **Source:** Identify the source of the drug or biologic to be used.

GUA pills will be obtained from Watson Pharmaceuticals by the Investigational Drug Service (IDS) at Yale-New Haven Hospital (YNHH). The research pharmacist will make up identical active and placebo capsules for medication administration for both sites. Medications will be shipped to Stony Brook from Yale for randomization and dispensing at the Stony Brook site. Medication administration will occur at 8am and 8pm each day to standardize the time of administration.

a) Is the drug provided free of charge to subjects? YES NO
If yes, by whom? IDS at YNHH

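### The pilot figures behind the sample size do not fit the stated pilot head count, 40 per arm does not follow from the women's effect, and f=0.25 is not detectable with over 80% power in a plain two-group test

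*Combined protocol and SAP*

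**What the plan says.** All places are in the combined protocol and SAP.

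- **Section I, item 13, Adequacy of Sample Size.** The paragraph first concedes that no clinical outcome study of guanfacine in women with SUD exists. It then quotes three pilot effects on cocaine-negative urines, placebo versus guanfacine: whole group 40.18% versus 67.86% (d=0.76); women "53.12% versus 100% for PBO vs. GUA in women" (d=1.0); and "35% vs 55% negative urines in placebo vs guanfacine in men" (d=0.628). From these it concludes, "assuming power=0.80" and alpha 0.05, that 40 per medication group are needed. It adds that 40 per group detects f=0.25 with more than 80% power, and allows 20% attrition to reach 50 per group.
- **Section I, item 13, Data Analysis.** "For the primary outcome, we will use significance level of 0.05". Neither sidedness nor the primary test is named.
- **Section II, part B, item 2, Background Information.** The pilot groups are given as guanfacine "n=7: 5M/2F) vs placebo (n=7: 4M/3F").
- **Section I, item 3, Background.** The pilot is said to have "led to higher cocaine-negative urines in an 8-week outpatient setting only in women and not men".

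**The concern.** The trial enrols women only, so a reader will take the women's pilot effect as the natural support for its size. That effect is printed without a sample size or interval, and the head count appears in another section and does not agree with the percentages. The paragraph moves from three effects to one number without saying which effect produced it, and the quoted detectable effect is smaller than a simple test on 40 per arm can deliver. At stake is what a null or modest result will mean. Someone relying on f=0.25 would believe the trial can rule out effects that it may well miss.

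**Working it through.** **Inputs.** Pilot percentages, d values, power 0.80, 40 per arm and 20% attrition come from Adequacy of Sample Size; alpha 0.05 from Data Analysis; pilot head counts from the drug background section. Two-sided testing is my assumption.

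**1. Head count against percentages** (equal weight per person: (men × men's % + women × women's %) / 7)

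- Guanfacine, 5M/2F: (5×55 + 2×100)/7 = 67.86. This matches the printed figure.
- Placebo, stated 4M/3F: (4×35 + 3×53.12)/7 = 42.77. The printed figure is 40.18.
- Placebo, 5M/2F: (5×35 + 2×53.12)/7 = 40.18. This matches.

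If urines were pooled rather than averaged per person, the women's share would have to be (40.18 − 35)/(53.12 − 35) = 0.286, which is 2/7. Three of seven people would be 0.429.

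Two side checks point the same way, each on an assumption the documents do not state:

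- *16 urines per person (two a week for 8 weeks).* 17/32 = 53.125%, 28/80 = 35% and 45/112 = 40.18% are whole counts at 5M/2F. Three women would need 0.5312 × 48 = 25.5 urines.
- *d on the pooled SD.* Two placebo women at 100% and 6.25% (mean 53.125) against two at 100% give pooled SD 46.875, difference 46.875 and d=1.00. With three placebo women at that mean, the widest spread is 100, 59.375 and 0, with SD 50.29. The pooled SD is then √(2×50.29²/3) = 41.06, so d is at least 46.875/41.06 = 1.14. If d used the placebo SD alone, the minimum would be 46.875/50.29 = 0.93 and d=1.0 would be possible with three women.

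**2. Precision of the women's effect** (taking d=1.0 as a pooled-SD value; t = d/√(1/n₁ + 1/n₂))

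| Women, guanfacine v placebo | t (df) | p | 95% CI for d |
|---|---|---|---|
| 2 v 2 | 1.00 (2) | 0.42 | −1.25 to 3.07 |
| 2 v 3 | 1.10 (3) | 0.35 | −1.01 to 2.88 |

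These are reconstructions from summary figures, not results from source data.

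**3. Where 40 comes from** (n per arm = 2(1.960 + 0.842)²/d² = 15.70/d², then the exact t-test)

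| Effect | Normal approximation | t-test | Power at 40 per arm (t-test) |
|---|---|---|---|
| Women, d=1.0 | 16 | 17 | 99% |
| Whole group, d=0.76 | 28 | 29 | 92% |
| Men, d=0.628 | 40 | 41 | 79% |

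The plan's 40 is reproduced only by the men's d, using the normal approximation, and 40/(1 − 0.20) = 50 reproduces the total. One-sided t-tests give 14, 23 and 33. A one-sided comparison of the whole-group proportions without continuity correction also gives 40, but the plan names no such test.

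**4. The f=0.25 claim** (two groups: d = 2f = 0.50)

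- Power at 40 per arm: 60% two-sided, 72% one-sided. Needed for 80% two-sided: 64 per arm by t-test.
- With no attrition, 50 per arm gives about 70% two-sided.
- Effect detectable at 40 per arm with 80% power, two-sided 0.05: d=0.634, f=0.317.
- Repeated measures, between-group effect, λ = 80 × 0.25² × m/(1 + (m−1)ρ). At ρ=0.5, power is 85% for m=10 and 86% for m=20. At ρ=0.7 it is 73% and 74%.

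**5. The sex statement.** The background sentence denies a urine benefit in men. The sample-size paragraph reports 55 − 35 = 20 percentage points in favour of guanfacine in men, d=0.628.

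**The case against.** The strongest defence is that the paragraph attributes 40 to no single effect and opens by admitting there are no outcome studies in women with SUD. Declining to size the trial on the largest and least precise effect is conservative: 40 per arm has about 99% power if d=1.0 is true. The paragraph also cites laboratory effects, from a study that included 13 women. All of this stands. A reader might infer that the sample size has no basis in women at all, or that it was taken from the men's result. The documents support neither. The laboratory data are data in women, though on craving and Stroop rather than urines, and the link to the men's d is an inference from arithmetic.

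It is also fair that the only head count on paper is three placebo women. A reader might conclude that the pilot had exactly two women per arm, one placebo woman being negative throughout and the other almost never. That needs an assumed urine schedule with none missing and a particular definition of d. The percentages point to two women but do not prove it.

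Finally, the outcome includes urines taken twice weekly over 10 weeks, so a repeated-measures test could justify f=0.25. It could, but the plan states neither the test nor the correlation, and the claim fails at a correlation of 0.7.

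**Conclusion.** The point holds as a reporting and justification fault. The placebo sex split and the percentages disagree (42.77% against 40.18%, with equal weight per person). The women's effect comes from two guanfacine women and two or three placebo women, and its interval spans zero widely on either count. The figure of 40 follows from neither the women's effect (17) nor the whole-group effect (29), and its source is unstated. For a two-group comparison at two-sided 0.05, power for f=0.25 is about 60%, and the detectable effect is d=0.63 (f=0.32). The background sentence on sex conflicts with the men's figures.

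This does not show that 40 per arm is too few; that depends on the true effect in women, which the pilot cannot tell us. Nor does it touch the laboratory sex-specific findings, which come from a different study. A reader might add that a women-only trial cannot test a sex difference, but none of the three stated aims is a sex comparison.

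**What to change.** 1. Check the pilot source data and reconcile the placebo sex split between Adequacy of Sample Size and the drug background section. Then report the women's pilot result with its actual n and confidence interval.
2. Replace the derivation of 40 with the effect, test and sidedness actually used. State that 40 analysed per arm detects d=0.63 (f=0.32) with 80% power at two-sided 0.05 in a two-group comparison. Keep f=0.25 only if the repeated-measures test, number of measures and assumed correlation are stated and deliver the claimed power. Say that the target effect is an assumption, not an estimate from women's pilot data.
3. Qualify or delete the restriction to women in the pilot-urine sentence of the Background. Leave the laboratory statements as they are.

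The cost is a look at the pilot data and text edits in three sections. N does not change. The stated justification becomes less favourable.

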HRP-503B – BIOMEDICAL RESEARCH PROTOCOL
(2017-1)

Protocol Title: Guanfacine to Improve Substance Use Outcomes in Women
HIC#: 2000023100

Principal Investigator: [name] PhD

Version Date: April 2018

(If applicable) **Clinicaltrials.gov Registration #:** Click or tap here to enter text.

SECTION I: RESEARCH PLAN

- Statement of Purpose:** State the scientific aim(s) of the study, or the hypotheses to be tested.

We hypothesize that Guanfacine (GUA) (3mg/day) will reduce drug craving, improve cognitive flexibility and result in associated lower drug use in women with substance use disorder (SUD) in an outpatient clinical setting. This study proposes to extend our previous Phase I experimental work to address the following specific aims: (1) assess GUA's target engagement of drug craving and cognitive flexibility in a laboratory challenge session and in a 10-week outpatient clinical study, (2) demonstrate target validation by showing that reduced drug craving and improved cognitive flexibility will predict lower drug use outcomes during the 10-week clinical trial in SUD women, and finally, (3) evaluate data replication and scalability of GUA target effects across two clinical sites (Yale and SUNY-Stony Brook).

- Probable Duration of Project:** State the expected duration of the project, including all follow-up and data analysis activities.
3 years followed by 2-years data analysis
- Background:** Describe the background information that led to the plan for this project. Provide references to support the expectation of obtaining useful scientific data.

Growing basic evidence indicates that the alpha-2 adrenergic agonist, guanfacine (GUA) decreases drug-related striatal-limbic up-regulation and stress sensitization resulting in drug cue and stress-induced reinstatement in laboratory animals (Shaham and Hope, 2005), and also improves neurocognitive abilities such as attention, flexibility, working memory and decision making (Arnsten, 2009). In NIDA-supported medications development work (R01-DA027130, PI: [name]), we identified in a 3-day inpatient laboratory controlled experiment that GUA at 3mg/day dose engaged target drug craving and cognitive flexibility processes, and more importantly, that GUA engaged these key processes in a sex-specific manner with

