Neutral Imagery Condition (Condition 2)	
3:40 PM	Schedule as in condition 1
Stress / Drug Cues (Condition 3)	
4:20 PM	Schedule as in condition 1

Order of imagery conditions is counterbalanced across subjects.

Study Assessments: Assessments include the following:

- 1) Sample description and eligibility including sociodemographics; psychosocial, substance use, and medical history; psychiatric assessment using the:
 - i) Structured Clinical Interview of Diagnostics (SCID-I) for DSM-V,(First et al., 1995),
 - ii) Connors ADHD Assessment and Rating Scale (CAARS,(Conners, 1999)
 - iii) vitals
 - iv) CBC, blood chemistry
 - v) urinalysis
 - v) pregnancy testing;
- 2) Primary SUD outcomes assessed using the:
 - i) Substance Use Calendar (SUC) developed by Miller and Del Boca (Miller and Del Boca, 1994) and based on the Time-Line Follow-Back (Sobell and Sobell, 1992; Sobell et al., 1996) and urinalysis for objective drug use assessed 2X/weekly during the 10 week period (20 urines);
- 3) Secondary Outcome Measures assessing drug craving using the standard brief versions of the Drug Craving questionnaires for cocaine (Cocaine Craving Questionnaire: CCQ,(Tiffany et al., 1993), cannabis (Marijuana Craving Questionnaire: MCQ, (Heishman et al., 2009)), alcohol (Alcohol Urges Questionnaire: AUQ, (Bohn et al., 1995) and nicotine (Questionnaire of Smoking Urges: QSU(Tiffany et al., 1993); (Tiffany and Drobes, 1991). Drug abstinence symptoms using standardized cocaine selective severity assessment (CSSA, (Kampman et al., 1998), Clinical Alcohol Withdrawal Assessment-Revised (Sullivan et al., 1989); The Cannabis Withdrawal Scale (Allsop et al., 2011); and the Minnesota Nicotine Withdrawal Scale (MNWS; (Hughes et al., 1986). Other drug use and drug related problems will be measured using the SUC; urinalysis; breathalyzer; the Addiction

Severity Index (ASI; (McLellan et al., 1992)) and Treatment Services Review (McLellan et al., 1992); stress (Perceived Stress Scale; (Cohen et al., 1983)); anxiety (Hamilton Anxiety Rating Scale, Ham-A; (Hamilton, 1960)) and depressive symptoms (Hamilton Depression Rating Scale, Ham-D, (Hamilton, 1960)). cognitive flexibility will be assessed using the Stroop Color Word Test; (Golden, 1975),

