Saliva: Cortisol saliva samples will be collected using salivette tubes placed between their tongue and cheek for approximately 2–3 min until the swab is completely saturated. Samples will immediately be placed in ice subsequent to storage at -80 degrees. All samples will be assayed in duplicate at the Yale Core Laboratories.

Contingency management for treatment attendance and behavioral support:

Twice weekly treatment attendance will be reinforced using standard contingency management (CM) procedures, which are known to greatly increase study compliance and attendance (Petry and Simcic, 2002; Roll et al., 2006; Stitzer and Petry, 2006). CM will be provided in the form of a “fishbowl” containing 500 chips. Half of the chips have no monetary value but are imprinted with “good job,” 219 chips have a value of \$1, 30 chips have a value of \$25, and 1 chip has a value of \$100. Upon completion of all requirements for a given visit, patients will receive fishbowl draws. Attendance at both weekly visits earns the patient bonus draws for that week. Failure to attend a visit without prior approval or failure to complete all visit requirements results in no draws earned for that visit and loss of bonus draws for that week. Participants will initially earn three draws per visit in week one with draws increasing by one each week. The weekly bonus draws will remain constant at 5 draws. Patients who attend all required visits will have the opportunity to make 264 draws from the fishbowl, for estimated earnings of \$725 over 3 months. Subjects will also participate in weekly (45 minute) manualized cognitive behavioral relapse prevention therapy (Carroll et al., 1991) integrated with Medication Management (MM), providing advice and support from medical practitioners concomitantly with dispensing medications, safety checking and compliance (Pettinati, 2004).

Relapse, c

5. Genetic Testing N/A

6. **Subject Population:** Provide a detailed description of the types of human subjects who will be recruited into this study.

One hundred treatment seeking women with SUD (50 per site)

7. **Subject classification:** Check off all classifications of subjects that will be specifically recruited for enrollment in the research project. Will subjects who may require additional safeguards or other considerations be enrolled in the study? If so, identify the population of subjects requiring special safeguards and provide a justification for their involvement.

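### The 80%-power sentence covers Aim 3 (replication across two sites), but the power figures are for medication main effects only; no Aim 3 analysis is stated, and 80% is not shown if Aim 3 is read by site

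*Combined protocol and SAP*

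**What the plan says.** The Statement of Purpose gives Aim 3 as to "evaluate data replication and scalability of GUA target effects across two clinical sites". In Section I, 13, Adequacy of Sample Size, the plan sets power at 0.80 and alpha at 0.05 and concludes that "we will need 40 subjects per cell (Medgroup) to assess GUA/PBO in clinical outcome hypotheses in Aim 2 and Aim 3". Two power statements follow:

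- more than 80% at f=0.25, alpha 0.05, "for the main effect of medication group on the primary outcome variable";
- f=0.28 at alpha 0.01, "with 80% power for all the main effects for secondary outcome variables".

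The 40 per group is raised for 20% attrition to 50 per group, 100 in total and 50 per site. That is the only place where site enters the sample-size text.

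The Data Analysis paragraph of the same section covers data checks, baseline comparison of the treatment groups, significance levels and one covariate rule: "If any group differences are found, the specific variable will be entered as a covariate in all specific analyses". It names no efficacy model. In the Research Plan, the Randomization paragraph lists age, education, race, ADHD and severity of drug use as balancing factors; site is not among them. Study Assessments puts urine testing at twice weekly for 10 weeks, 20 urines in all, under the primary outcomes.

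**The concern.** One of three specific aims is presented as powered, but the power given is for a different question. A pooled medication effect can be well powered while a statement about each site, or about the difference between sites, is not. With no site term or criterion fixed in advance, what counts as replication can be settled after the data are seen. One site could miss significance by chance and be read as a failure to replicate, or a non-significant interaction could be read as success.

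The outcome for Aim 3 is also unsettled: the Statement of Purpose speaks of effects on the targets (craving and cognitive flexibility), whereas the sample-size text speaks of clinical outcomes.

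**Working it through.** **Inputs from the plan.** 40 evaluable per group (N=80); f=0.25 at alpha 0.05; f=0.28 at alpha 0.01; 20% attrition; 50 women per site; 20 urines.

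**Assumptions.** Two-sided tests; 1:1 allocation within site; equal attrition; urine results treated as continuous. For two groups d=2f, so f=0.25 is 0.5 SD.

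**Cell size by site.** 50 × 0.8 / 2 = 20 completers per arm, so N=40 in one site.

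**Formula.** Noncentral F with 1 numerator df, N−2 denominator df and λ = f²·N/DE. DE=1 for one outcome per woman. For the average of m measurements with correlation ρ, DE = (1+(m−1)ρ)/m.

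**Step 1: the plan's pooled figures.** With DE=1 and N=80:

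- f=0.25, alpha 0.05: λ = 0.0625 × 80 = 5.0, power 60%.
- f=0.28, alpha 0.01: λ = 0.0784 × 80 = 6.27, power 45%.

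Neither stated figure is reproduced. A plain test reaches 80% at about d=0.63 (alpha 0.05). With m=20 and an assumed ρ=0.5, DE = 10.5/20 = 0.525 and power is 86% and 79%, close to what is stated. So a repeated-measures basis would explain both figures, but the plan states neither that model nor the correlation.

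**Step 2: one site at f=0.25, alpha 0.05.**

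| Basis | DE | Pooled, N=80 | One site, N=40 |
|---|---|---|---|
| Plain two-group test | 1 | 60% | 34% |
| Pooled power exactly 80% | 0.621 | 80% | 50% |
| 80% at f=0.28, alpha 0.01 taken as true | 0.514 | 87% | 57% |
| 20 urines, ρ=0.7 (assumed) | 0.715 | 74% | 45% |
| 20 urines, ρ=0.5 (assumed) | 0.525 | 86% | 57% |
| 20 urines, ρ=0.2 (assumed) | 0.240 | 99% | 88% |

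The third row solves 80% at f=0.28, alpha 0.01, N=80, giving λ=12.19 and DE = 6.27/12.19 = 0.514. In one site λ = 0.0625 × 40/0.514 = 4.86, hence 57%. With all 50 women per site analysed, λ = 0.0625 × 50/0.514 = 6.08 and power is 68%.

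To reach 80% in one site at f=0.25, DE must be 0.302. With 20 urines that means ρ = (20 × 0.302 − 1)/19, about 0.27 or lower.

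**Step 3: larger effects, plain two-group test, 20 per arm.**

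- d=0.76 (whole-group pilot): 65%.
- d=1.0 (women's pilot): 87%. The pilot in Background Information had 2 women on guanfacine and 3 on placebo.
- f²=0.39 (lower end of the target-engagement effects in the sample-size text): λ = 0.39 × 40 = 15.6, power 97%.

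**Step 4: precision and the between-site difference.** The 95% CI half-width is t × √(2·DE/20) for one site (38 df) and t × √(4·DE/20) for the difference between sites (76 df).

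- DE=1: 0.64 SD and 0.89 SD.
- DE=0.514: 0.46 SD and 0.64 SD.

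A between-site difference of 0.5 SD, the whole planned effect, has power of 20% and 34% respectively.

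**The case against.** The strongest reply is that the plan defines its cell as the medication group, not site by medication, and at once limits the power to the medication main effect. On that reading Aim 3 rests on the pooled two-site sample and the pooled figure applies. This reading is open. It is not stated, and replication across sites is not an obvious name for a pooled comparison.

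Second, nothing in the plan requires significance at each site, so within-site power measures a test that is not proposed. That is fair. The figures show only what the quoted 80% would mean if Aim 3 were judged that way.

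Third, Aim 3 as worded in the Statement of Purpose concerns target effects, for which the plan cites f² of 0.39 to 1.22; at 0.39 one site would have 97% power. This counts against any flat claim of a shortfall. But those are sex-by-medication effects from earlier laboratory work in men and women (Background Information describes 29 men and 13 women), not a medication effect among women.

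Fourth, a reader might infer that the plan's own figures imply 57% within a site. They do not by themselves. That number carries a design effect from the secondary-outcome statement to the primary outcome, although urines are taken 20 times and the laboratory challenge is run twice. The primary statement, more than 80%, is a lower bound and fixes only a floor of about 50%.

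Fifth, a reader might infer that the covariate rule can never bring site into the model. That holds only if arms are balanced within site. Site is not a listed balancing factor, so a chance imbalance could trigger the rule. Even then, a covariate is not a treatment-by-site contrast.

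Finally, no efficacy model is named for any aim. That is true, but Aim 3 is where the stated power and the stated question differ.

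**Conclusion.** The point holds in a conditional form. The plan attaches 80% power to an aim about two sites, supports it only with main-effect power, and states no analysis for that aim.

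Read by site at f=0.25, 80% is not shown. The results run from 34% on a plain test, through 50% and 57% on the bases that use the plan's power statements, to 88% under a low assumed correlation. They rest on 20 completers per arm per site. At that effect, 80% needs a design effect of about 0.30 or less; otherwise it needs a larger effect, and the larger effects cited rest on five women or on sex-by-medication contrasts.

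The documents do not support saying that Aim 3 is underpowered outright, because they do not say what Aim 3 tests. Nor do they support saying that the pooled power is wrong: 60% and 45% apply only if no repeated-measures model lies behind the stated figures. The pooled design itself is not called into question. This should be corrected, mainly in wording.

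**What to change.** 1. Limit the 80%-power sentence to the pooled medication main effect and take Aim 3 out of it, or state that Aim 3 is the pooled two-site comparison.
2. If Aim 3 compares sites, name its outcome and describe it as estimation. Fit treatment, site and treatment-by-site, and report each site's effect and the between-site difference with 95% CIs, giving the expected half-widths. State that neither site-level p-values nor a non-significant interaction will be taken as proof for or against replication.
3. Give the repeated-measures model, number of measurements and correlation behind f=0.25 and f=0.28. If there is none, restate the power as about 60% and 45%, with 80% reached at about d=0.63 for the primary outcome.

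The cost is a few sentences and one extra model, with no additional patients. The drawback is that the stated power becomes less favourable for Aim 3 if it is read by site, and for the pooled tests if no repeated-measures basis exists.
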